## 8.2 Serious Adverse Events

The SAE definition and reporting requirements are in accordance with the International Conference of Harmonisation (ICH) Guideline for Clinical Safety Data Management: Definitions and Standards for Expedited Reporting, Topic E2A.

An SAE is defined as any untoward medical occurrence that at any dose:

- Result in death
- Is immediately life-threatening (ie, in the opinion of the investigator, the AE places the subject at immediate risk of death; it does not include a reaction that, had it occurred in a more severe form, might have caused death)
- Requires inpatient hospitalization or results in prolongation of an existing hospitalization
- Results in persistent or significant disability or incapacity:
  - Note: The term “disability” refers to events that result in a substantial disruption of a subject’s ability to conduct normal life function.
- Is a congenital anomaly or birth defect
- Is an important medical event (IME)
  - Note: The term “important medical event” refers to an event that, based upon appropriate medical judgment, may not be immediately life-threatening or result in death or hospitalization, but may jeopardize the subject or require intervention to prevent one of the other serious outcomes listed under the definition of SAE. Examples of IMEs include intensive treatment in an emergency room or at home for allergic bronchospasm; blood dyscrasias, or convulsions that do not result in hospitalization; or development of product dependency or product abuse.

## 8.3 Serious Adverse Event Reporting

As soon as an investigator becomes aware of an AE that meets the definition of ‘serious,’ this should be documented to the extent that information is available.

Investigator shall notify Exelixis within twenty-four (24) hours of making such discovery by submitting a completed SAE report form and any other pertinent SAE information as indicated on the SAE reporting form.

For multicenter studies the Investigator must notify the IND/CTA Sponsor by submitting a completed SAE report form and any other pertinent SAE information as indicated on the SAE reporting form within 24 hours to allow the IND/CTA Sponsor to submit the SAE report form to Exelixis no later than 2 business days.

This report must be submitted by Institution to Exelixis at e-mail: [[contact]](mailto:[contact]) or [contact], even if it is not felt to be drug related.

Pregnancy (for a subject or for the partner of a subject), although not itself an SAE, should also be reported on a pregnancy form and be followed up to determine outcome,

including spontaneous or voluntary termination, details of birth, and the presence or absence of any birth defects or congenital abnormalities

SAEs that must be recorded on an SAE Reporting form include the following:

- all SAEs that occur after informed consent and through 30 days after the decision to discontinue study treatment (or the date the subject is deemed to be a screen failure)
- any SAEs assessed as related to study treatment or study procedures, even if the SAE occurs more than 30 days after the decision to discontinue study treatment

Although most hospitalizations necessitate reporting of an SAE, some hospitalizations do not require SAE reporting, as follows:

- elective or previously scheduled surgeries or procedures for pre-existing conditions that have not worsened after initiation of treatment (eg, a previously scheduled ventral hernia repair)
- pre-specified study hospitalizations for observation
- events that result in hospital stays of fewer than 24 hours and that do not require admission (eg, an emergency room visit for hematuria that results in a diagnosis of cystitis and discharge to home on oral antibiotics).

SAEs must, however, be reported for any surgical or procedural complication resulting in prolongation of the hospitalization.

Adverse event terms recorded on the CRFs will be mapped to preferred terms using the Medical Dictionary for Regulatory Activities (MedDRA). Seriousness, severity grade and relationship to study treatment will be assessed by the investigator. Severity grade will be defined by the National Cancer Institute (NCI) CTCAE v5.0. Listings of AEs will be provided.

#### 8.4 Regulatory Reporting

The Investigator will assess the expectedness of each related SAE. The current cabozantinib Reference Safety Information (Investigator Brochure) will be used as the reference document for assessing the expectedness of the event with regard to cabozantinib. All serious unexpected adverse drug reactions (unexpected related SAEs) must be reported to all appropriate regulatory authorities and Ethics Committees by the investigator as required by 21 CFR 312.32 or by Directive 2011/20/EC:

- These reports are to be filed utilizing the Form FDA 3500A (MedWatch Form) or a CIOMS-1 form.
- The final MedWatch Form or CIOMS-1 form must be submitted by the study site to Exelixis within one to two business days of submission to the FDA or applicable regulatory agency (including confirmation of date that the report was submitted) to allow Exelixis time to cross-report to Exelixis' IND. E-mail: [[contact]](mailto:[contact]); [contact].

- Exelixis reserves the right to upgrade the Investigator assessment of an SAE based on Sponsor reporting responsibilities.

## 9. Other Safety Considerations

### 9.1 Laboratory Data

All laboratory data required by this protocol and any other clinical investigations should be reviewed. Any abnormal value that leads to a change in subject management (eg, dose reduction or delay or requirement for additional medication or monitoring) or that is considered to be of clinical significance by the investigator should be reported as an AE or SAE as appropriate.

### 9.2 Pregnancy

If a subject becomes pregnant during the study, she will be taken off study treatment and will be followed through the end of her pregnancy. The investigator must inform the Sponsor of the pregnancy. Forms for reporting pregnancies will be provided to the study sites upon request. The outcome of a pregnancy (for a subject or for the partner of a subject) and the medical condition of any resultant offspring must be reported to Exelixis or designee. Any birth defect or congenital anomaly must be reported as an SAE, and any other untoward events occurring during the pregnancy must be reported as AEs or SAEs, as appropriate.

### 9.3 Medication Errors/Overdose

Any study drug administration error or overdose that results in an AE, even if it does not meet the definition of serious, requires reporting within 24 hours to Exelixis or designee.

### 9.4 Follow-Up of Adverse Events

Any related SAEs or any AEs assessed as related that led to treatment discontinuation, including clinically significant abnormal laboratory values that meet these criteria, ongoing 30 days after the decision to discontinue study treatment must be followed until either resolution of the event or determination by the investigator that the event has become stable or irreversible. This follow-up guidance also applies to related SAEs that occur **> 30 days after the decision to discontinue** study treatment. The status of all other continuing AEs will be documented as of 30 days after the decision to discontinue study treatment.

## 10. Data Forms and Submission Schedule

Study data will be collected and stored in OnCore®, developed by Forte Research Systems, Inc. ([www.forteresearch.com](http://www.forteresearch.com)). OnCore® Enterprise Research is a comprehensive, web-based, Clinical Trial Management System (CTMS) which utilizes an Oracle database. It has been licensed by Indiana University (IU) to support the operations and data capture of clinical research trials. The system has been installed and configured within a HIPAA-aligned, Information Technology (IT), operations center supported by IU's IT organization, University Information Technology Services (UITS). OnCore® provides users secure access with unique IDs/passwords and restricts access by assigned roles, from any location, to record, manage, and report on data associated with the operation and conduct of clinical trials. The system is comprised of three specific applications—Clinical Research Management (CRM), Biospecimen Management (BSM), and Unified Registries Management (URM). Indiana University leverages OnCore® to support clinical research operations specifically as it relates to the following functions/processes: electronic Scientific Review Committee (SRC), regulatory management, protocol and subject life cycle management, coverage analysis, study financials management, subject registration and visit management, subject safety monitoring, protocol deviation monitoring, study auditing and monitoring, electronic data management, correlative study sample management, specimen banking and management, registries management, effort tracking, and reporting.

## 11. Data Safety Monitoring

This study will be conducted in accordance with the IU Simon Cancer Center Institutional DSMP for High Risk Trials.

Investigators will conduct continuous review of data and subject safety. Weekly review meetings for high risk trials are required and will include the principal investigator, clinical research specialist and/or research nurse (other members per principal investigator's discretion). Weekly meeting summaries should include review of data and subject safety by including for each dose level: the number of subjects, significant toxicities as described in the protocol, dose adjustments and responses observed. Study teams should maintain meeting minutes and attendance for submission to the DSMC upon request.

### **Data and Safety Monitoring Committee**

The IUSCC Data and Safety Monitoring Committee (DSMC) is responsible for oversight of subject safety, regulatory compliance, and data integrity for this trial. The DSMC will review this study semi-annually to review overall trial progress, toxicity, compliance, data integrity, and accrual per the Institutional DSMP.

Furthermore, the DSMC conducts an administrative review of serious adverse events (SAEs), deviations, reportable events, and any other outstanding business. Major issues may require further DSMC review or action.

For any increase in frequency of grade 3 or above adverse events (above the rate reported in the Investigator Brochure or package insert), the principal investigator will notify the DSMC Chair immediately. The notification will include the incidence of study adverse events, grades, and attributions, as well as investigator statements regarding comparison with risks per the IB/ package insert.

At any time during the conduct of the trial, if it is the opinion of the investigators that the risks (or benefits) to the subject warrant early closure of the study, the DSMC Chair and Compliance Officer must be notified within 1 business day via email, and the IRB must be notified within 5 business days. Alternatively, the DSMC may initiate suspension or early closure of the study based on its review.

### **IND Annual Reports**

For trials with an IND held locally by the IU principal investigator or university, the IND Annual Report will be prepared and submitted to the Compliance Team. This report will be reviewed by the DSMC at the time of FDA submission.

### **Study Auditing and Monitoring**

All trials conducted at the IUSCC are subject to auditing and/or monitoring per the Institutional DSMP. Reports will be reviewed by the full DSMC at the time of study review.

### **Data Management/ Oncore Reporting Requirements**

The DSMC reviews data and study progress directly from Oncore; therefore, timely data entry and status updates are vital. Study data must be entered within Oncore promptly, no later than one week from study visit occurrence. Subject status in Oncore will be updated in real time, as this may affect overall trial enrollment status. Global SAEs and deviations will be reviewed on a monthly basis by the DSMC Chair directly from Oncore.

### **Study Accrual Oversight**

Accrual data will be entered into the IU Simon Cancer Center OnCore system. The Protocol Progress Committee (PPC) reviews study accrual twice per year, while the PPC coordinator reviews accrual quarterly.

### **Oncore Safety Reporting**

In addition to protocol- and regulatory-required safety reporting, all serious adverse events (SAEs) will be captured in the Oncore system within 1 business day of notification. Initial SAE reporting will include as much detail as available, with follow-up to provide complete information. Attributions will be assessed to study drugs, procedures, study disease, and other alternate etiology.

### **Protocol Deviation Reporting**

Protocol deviations will be entered into OnCore within 5 days of discovery and reviewed by the DSMC Chair on a monthly basis. Findings will be reported to the full DSMC at the

time of study review. For serious or repetitive protocol deviations, additional action may be required by the DSMC.

## 12. Study Withdrawal/Discontinuation

Reasons for a patient to not complete the study:

- a) Death
- b) Disease progression
- c) Lost to follow-up
- d) Entry into another therapeutic study
- e) Patient request to withdraw from clinical trial
- f) Manufacturing limitations on drug supplies
- g) Adverse events requiring removal from study
- h) Pregnancy
- i) Breastfeeding
- j) Non-compliance that in the opinion of the investigator does not allow for ongoing participation
- k) Physician determines that it is not in the patient's best interest
- l) Subject develops DVT and requires anticoagulation therapy

## 13. Evaluations

Response criteria are assessed based on the product of the longest diameter and its longest perpendicular diameter. Development of new disease or progression in any established lesions is considered progressive disease, regardless of response in other lesions. Response criteria are based on the Glioblastoma and Response Assessment in Neuro-Ocology (RANO) Criteria.

Response criteria will be assessed by an independent radiologist [name].

Complete response (CR): Complete response requires all of the following: complete disappearance of all enhancing measurable and non-measurable disease sustained for at least 4 weeks; no new lesions; stable or improved non-enhancing (T2/FLAIR) lesions; and patient must be off corticosteroids or on physiologic replacement doses only, and stable or improved clinically. In the absence of a confirming scan 4 weeks later, this response will be considered only stable disease.

Partial response (PR): Partial response requires all of the following:  $\geq 50\%$  decrease, compared with baseline, in the sum of products of perpendicular diameters of all measurable enhancing lesions sustained for at least 4 weeks; no progression of non-measurable disease; no new lesions; stable or improved non-enhancing (T2/FLAIR) lesions on same or lower dose of corticosteroids compared with baseline scan; and patient must be on a corticosteroid dose not greater than the dose at time of baseline

scan and is stable or improved clinically. In the absence of a confirming scan 4 weeks later, this response will be considered only stable disease.

Stable disease (SD): Stable disease occurs if the patient does not qualify for complete response, partial response, or progression (see next section) and requires the following: stable non-enhancing (T2/FLAIR) lesions on same or lower dose of corticosteroids compared with baseline scan and clinically stable status. In the event that the corticosteroid dose was increased for new symptoms and signs without confirmation of disease progression on neuroimaging, and subsequent follow-up imaging shows that this increase in corticosteroids was required because of disease progression, the last scan considered to show stable disease will be the scan obtained when the corticosteroid dose was equivalent to the baseline dose.

#### Progressive Disease (PD):

Progression is defined by any of the following:  $\geq 25\%$  increase in sum of the products of perpendicular diameters of enhancing lesions (compared with baseline if no decrease) on stable or increasing doses of corticosteroids; a significant increase in T2/FLAIR non-enhancing lesions on stable or increasing doses of corticosteroids compared with baseline scan or best response after initiation of therapy, not due to comorbid events; the appearance of any new lesions; clear progression of non-measurable lesions; or definite clinical deterioration not attributable to other causes apart from the tumor, or to decrease in corticosteroid dose. Failure to return for evaluation as a result of death or deteriorating condition should also be considered as progression.

Increase in corticosteroid dose alone, in the absence of clinical deterioration related to tumor, will not be used as a determinant of progression. Patients with stable imaging studies whose corticosteroid dose was increased for reasons other than clinical deterioration related to tumor do not qualify for stable disease or progression. They should be observed closely. If their corticosteroid dose can be reduced back to baseline, they will be considered as having stable disease; if further clinical deterioration related to tumor becomes apparent, they will be considered to have progression. The date of progression should be the first time point at which corticosteroid increase was necessary.

The definition of clinical deterioration is left to the discretion of the treating physician, but it is recommended that a decline in the KPS from 100 or 90 to 70 or less, a decline in KPS of at least 20 from 80 or less, or a decline in KPS from any baseline to 50 or less, for at least 7 days, be considered neurologic deterioration unless attributable to comorbid events or changes in corticosteroid dose. Similarly, a decline in the Eastern Cooperative Oncology Group and WHO performance scores from 0 or 1 to 2 or 2 to 3 would be considered neurologic deterioration.

Patients with non-measurable enhancing disease whose lesions have significantly increased in size and become measurable (minimal bidirectional diameter of  $\geq 10$  mm and visible on at least two axial slices that are preferably, at most, 5 mm apart with 0-mm skip) will also be considered to have experienced progression. The transition from a

non-measurable lesion to a measurable lesion resulting in progression can theoretically occur with relatively small increases in tumor size (eg, a 9 × 9 mm lesion [non-measurable] increasing to a 10 × 11 mm lesion [measurable]). Ideally, the change should be significant (> 5 mm increase in maximal diameter or ≥ 25% increase in sum of the products of perpendicular diameters of enhancing lesions). In general, if there is doubt about whether the lesion has progressed, continued treatment and close follow-up evaluation will help clarify whether there is true progression.

If there is uncertainty regarding whether there is progression, the patient may continue on treatment and remain under close observation (eg, evaluated at 4-week intervals). If subsequent evaluations suggest that the patient is in fact experiencing progression, then the date of progression should be the time point at which this issue was first raised. (Appendix VII)

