## **Exclusion Criteria**

1. Pregnancy or Breast-Feeding: Pregnant or breast-feeding women will not be entered on this study due to risks of fetal and teratogenic adverse events as seen in animal/human studies. Pregnancy tests must be obtained in girls who are post-menarchal. Males or females of reproductive potential may not participate unless they have agreed to use two methods of birth control- a medically accepted barrier method of contraceptive method (e.g., male or female condom) and a second effective method of birth control- during protocol therapy and for at least 4 months after the last dose of cabozantinib. Abstinence is an acceptable method of birth control.
2. Concomitant Medications:
  - a. Corticosteroids: Patients receiving corticosteroids who have not been on a stable or decreasing dose of corticosteroid for at least 7 days prior to enrollment are not eligible.
  - b. Investigational drugs: Patients who are currently receiving another investigational drug are not eligible.
  - c. Anti-cancer agents: patients who are currently receiving other anti-cancer agents are not eligible.
  - d. CYP3A4 active agents: Patients must not be receiving any of the following potent CYP3A4 inducers or inhibitors: erythromycin, clarithromycin, ketoconazole, azithromycin, itraconazole, grapefruit juice or St. John's wort. A list of other known CYP3A4 inducers and inhibitors that should be discontinued prior to initiation of protocol therapy and should be avoided during study therapy if reasonable alternatives exist is included in Appendix V.
  - e. Patients who are receiving systemic therapeutic treatment anticoagulation are not eligible. Patients receiving prophylactic systemic anticoagulation will be allowed with heparin or LMWH as long as eligibility PT/INR requirements are met. Concomitant anticoagulation with oral anticoagulations (e.g. warfarin, direct thrombin and Factor Xa inhibitors) or platelet inhibitors (eg. Clopidogrel) are not allowed.
  - f. Enzyme-inducing anticonvulsants: Patients must not have received enzyme-inducing anticonvulsants within 14 days prior to enrollment (See Appendix III for a list of unacceptable enzyme inducing anticonvulsants).
  - g. QTc Agents: Patients who are receiving drugs that prolong QTc are not eligible (See Appendix IV for a list of agents).
3. Patients must be able to swallow intact tablets. Patients who cannot swallow intact tablets are not eligible.

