Appendix VII: Summary of RANO Response Criteria

Criterion	Complete Response	Partial Response	Stable Disease	Progressive Disease
T1 enhancing disease	None	≥ 50% ↓	< 50% ↓ but < 25% ↑	≥ 25% ↑*
T2/FLAIR	Stable or ↓	Stable or ↓	Stable or ↓	↑*
New lesion	None	None	None	Present*
Corticosteroids	None	Stable or ↓	Stable or ↓	NA†
Clinical status	Stable or ↑	Stable or ↑	Stable or ↑	↓*
Requirement for response	All	All	All	Any*

\* Progression occurs when this criterion is present.

† Increase in corticosteroids alone will not be taken into account in determining progression in the persistent clinical deterioration.

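### Section 13 and Appendix VII give opposite classifications, SD and PD, for enhancing growth of 25% or more during a steroid taper, and neither is given precedence

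*Combined protocol and SAP*

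**What the plan says.** Section 13 (Evaluations) attaches a qualifier to the 25% enhancing-growth criterion for PD: "compared with baseline if no decrease) on stable or increasing doses of corticosteroids". Three other routes to PD carry no requirement that the dose be stable or rising: "the appearance of any new lesions; clear progression of non-measurable lesions; or definite clinical deterioration not attributable to other causes apart from the tumor". (Clinical decline caused by a steroid decrease is excluded.)

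The SD definition in Section 13 is residual: "Stable disease occurs if the patient does not qualify for complete response, partial response, or progression (see next section) and requires the following". The conditions that follow are "stable non-enhancing (T2/FLAIR) lesions on same or lower dose of corticosteroids compared with baseline scan and clinically stable status". None of them limits enhancing growth.

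Appendix VII tabulates the same categories. For SD, every row must be met, and the enhancing-disease row requires growth below 25%. For PD, any one row is enough. Growth of 25% or more carries an asterisk, explained as "Progression occurs when this criterion is present", and the steroid row for PD is marked not applicable.

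Section 14.6 estimates the disease control rate (complete or partial response, or SD lasting six months or more) with an exact 95% binomial interval. It also plans Kaplan-Meier estimates of PFS.

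**The concern.** A reader who applies Section 13 and a reader who applies Appendix VII can look at the same scan and record opposite results. The literal Section 13 reading errs towards apparent benefit, and there is no control arm in which the same scoring would operate.

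The situation is foreseeable. The corticosteroid exclusion in Section 5 admits patients on a "stable or decreasing dose of corticosteroid for at least 7 days prior to enrollment". Section 2.2 reports reduced steroid use in the adult glioblastoma study, and steroid use is the second secondary aim in Section 3.

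Section 13 already deals with the mirror image. When imaging is stable but steroids were raised for reasons other than tumour-related deterioration, the patient is placed in neither SD nor PD until the matter resolves. Growth while steroids are falling has no such provision.

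The primary efficacy estimate is at stake, and with it the pilot response data that Section 17 says are wanted before a larger trial is considered.

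**Working it through.** **Plan's own figure.** The plan gives no number for this rule. Its one design calculation is the Section 14.4 table for n = 10, which reproduces. The formula 1 − (1 − p)^10 at p = 0.05, 0.10, 0.15, 0.20, 0.25 and 0.30 gives 0.401, 0.651, 0.803, 0.893, 0.944 and 0.972, against the stated 0.40, 0.65, 0.80, 0.89, 0.94 and 0.97. The point does not depend on it.

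**Classification.** Take a patient whose steroid dose is falling, with stable T2/FLAIR, stable clinical status, no new lesion and no clear progression of non-measurable disease.

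- Section 13: the steroid condition on the 25% criterion is not met and no other PD trigger is present, so the scan is not PD. It is not CR or PR. The T2/FLAIR, steroid-dose and clinical conditions for SD are met, so the scan is SD.
- Appendix VII: growth of 25% or more fails the SD row and is enough for PD by itself.

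| Enhancing growth on a falling dose | Section 13, literal | Appendix VII |
|---|---|---|
| 10% | SD | SD |
| 24% | SD | SD |
| 25% | SD | PD |
| 40% | SD | PD |
| 100% | SD | PD |

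The texts agree below 25% and conflict from 25% upwards. On a stable dose Section 13 also gives PD from 25%, so the conflict is confined to the taper.

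**Effect on the disease control rate.** Inputs are n = 11 (Section 6) and n = 10 (Section 14.4). One patient moved between success and failure shifts the rate by 1/n: 1/11 = 9.1 points and 1/10 = 10.0 points. A smaller efficacy population under Section 14.3.3 would make each patient weigh more.

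The illustration below uses exact intervals: lower limit = Beta quantile at 0.025 with parameters (x, n − x + 1); upper limit = Beta quantile at 0.975 with parameters (x + 1, n − x).

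| n | One success | Two successes |
|---|---|---|
| 10 | 10.0% (0.3 to 44.5) | 20.0% (2.5 to 55.6) |
| 11 | 9.1% (0.2 to 41.3) | 18.2% (2.3 to 51.8) |

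**Frequency.** This cannot be computed. The documents do not say how many patients will be on steroids, how many will taper across a scan, or how many of those will show growth of 25% or more with everything else stable.

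**The case against.** The strongest objection is that the plan does limit growth in SD. Appendix VII sets the limit, and Section 13 refers to that appendix at its close. A reader might infer from Section 13 alone that SD has no growth limit anywhere and that a tumour growing by any amount on a taper will be scored as stable. The documents do not support that. Appendix VII excludes growth of 25% or more from SD, growth below 25% is SD under both texts and is no defect, and even Section 13 gives SD only when the other conditions hold. This part of the objection stands and confines the point to a contradiction. It does not remove it: no precedence is stated, the appendix is titled a summary, and the reference to it follows the paragraph on uncertain progression.

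Second, Section 13 says "Development of new disease or progression in any established lesions is considered progressive disease, regardless of response in other lesions". That does not settle the case, because what counts as progression is defined in the paragraph that carries the steroid qualifier.

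Third, Section 13 allows continued observation when progression is uncertain, with the date set back to when the question first arose, and an independent radiologist assesses response. This helps only if the case is regarded as uncertain. Literal Section 13 returns a definite SD.

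Fourth, the qualifier looks deliberate, since clinical decline caused by a steroid decrease is also excluded from PD. That is a fair reason to keep some allowance for tapering, but not to have two texts that disagree about it.

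Fifth, not every affected scan produces a false six-month success. Scans are three months apart, and once the dose stops falling, Section 13 itself can call the growth PD, although it does not say over what interval the dose must be stable. This stands: the per-patient shift applies only where the taper scan decides the six-month status.

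**Conclusion.** The contradiction is real and should be resolved. For enhancing growth of 25% or more on a falling steroid dose, with the other SD conditions met, Section 13 gives SD and Appendix VII gives PD.

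The supportable size is 9.1 points (n = 11) or 10.0 points (n = 10) on the disease control rate for each patient whose six-month status turns on the choice of text. PFS timing is affected on the assumption that PFS uses the Section 13 progression definition; Section 14.6 does not define the event.

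A reader might go further and conclude that the disease control rate and PFS are inflated by some stated amount. The documents do not support that. They contain no frequency, any figure would be a product of assumed proportions, and a radiologist who follows Appendix VII would introduce no upward error. The defect is that the result depends on an unstated choice between two texts.

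**What to change.** Two linked edits, confined to endpoint scoring:

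1. In the Section 13 definition of SD, add the Appendix VII condition: an increase of less than 25% in the sum of products for enhancing lesions.
2. Reconcile the Section 13 PD wording with the PD column of Appendix VII, so that both give one endpoint classification for growth of 25% or more on a decreasing dose. The first edit alone would leave such a scan neither SD nor PD in Section 13 while it remained PD in the appendix.

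If the sponsor prefers to hold the case as unresolved until a later scan, say so in both places, apply the back-dating rule that Section 13 already has for uncertain progression, and state how the case counts in the disease control rate. Section 14.6 has no unresolved category.

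Because progression also ends therapy (Sections 2.2.3 and 12), any effect of the wording on stopping treatment is for the sponsor to reconcile. No treatment rule is proposed here.

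The cost is a few sentences. No extra scan is required, and steroid diaries are already collected under Section 7. The downside is that the disease control rate may come out slightly lower, and an occasional six-month status may be settled later. A case left open at the Cycle 6 MRI, for example, could wait for the one at Cycle 9.
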